Repeat ablation procedures for left atrial arrhythmia (AF, AT or AFL of unknown origin*) within the 12-month FU period

- Percentage of subjects with repeat ablation during blanking period (≤ 90 days post index ablation procedure)
- Percentage of subjects with repeat ablation after blanking period (Day 91 – 365 post index ablation procedure)
- Percentage PV reconnection observed during repeat ablation procedures by targeted PVs treated at index ablation procedure and by subject
- Percentage of subject with repeat ablations due to non-PV targets

Quality of Life (QoL): the change of QoL assessed by comparing the Atrial Fibrillation Effect on Quality-of-Life (AFEQT™) scores before and at 3, 6 and 12- months after the ablation procedure.

Hospitalization for cardiovascular events through 12 months follow-up compared to 12 months prior to baseline.

***NOTE:** hospitalization is defined as prolonged stay > 2 nights post index ablation procedure or in-patient stay not concurrent with index ablation procedure > 1 calendar day; Excluding emergency room visits that do not result in admission to the hospital. Excluding social or administrative reasons for (prolonged) hospitalization.*

**AFL of unknown origin is defined as all AFL except those CTI dependent AFL as confirmed by 12-lead electrocardiogram (ECG) or entrainment maneuvers in an EP study.*

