13.2 Baseline Evaluation and Procedures

13.2.1 Pre-Procedure/Baseline Assessments

Below pre-procedure assessments and data collection must be performed prior to the ablation procedure.

- **Patient Information and Consent** (procedure must be done within 60 days of consent)
- **Demographics** (age, gender, etc.).
- **Medical history**, including but not limited to arrhythmia, heart disease, thromboembolic events, lung/respiratory problems.
 - **AF history** (first evidence of AF, number of episodes, symptoms, etc.).
 - **NYHA Functional Class Scale**.
 - **CHA₂DS₂ VASc Score** Subjects will be scored against the CHA₂DS₂ VASc.
 - **Vital signs** (length, weight, etc.)
 - **Cardiovascular Hospitalization history**: information on hospitalization for cardiovascular reason (including arrhythmia, cardioversion, ...) from 12 months prior to enrollment will be collected from medical records and recorded in the eCRF.
 - **Medication history**: Medication history (cardiac medication, AAD medication, anticoagulation regimen and any other clinically significant medication history) shall be gathered by interview or from medical records following enrolment but prior to the ablation procedure and should be recorded in the eCRF.
- **Pregnancy test** must be done on all women of childbearing age and potential within 72-hours prior to the procedure and documented in the subject's medical chart.
- **Imaging (TTE or other acceptable equivalent cardiac imaging – i.e., CT/MRA) within 6 months prior to procedure to assess the LA and LVEF.** Must be collected within 6 months prior to procedure, in case of the imaging assessment is older than 6 months LA/LVEF, dimensions shall be re-measured during the index ablation procedure prior to insertion of the study catheter. In case of re-measurements before study catheter insertion fail to meet the LA and/or LVEF criteria, the subject will be considered as not meeting eligibility and will be excluded.

- Imaging for **detection of left atrial thrombus** or other structural contraindications to an ablation procedure is mandatory the day before or on the day of the ablation procedure. Presence of a thrombus will require postponement of the ablation procedure or may even lead to exclusion of the subject from further study involvement. The imaging method to be used for atrial thrombus detection is TEE, Intracardiac Echocardiography (ICE), Cardiac CT or MRI

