13.3.6 Pre-Discharge Assessments

Prior to hospital discharge, the following assessments should be performed:

- **Medication regimen** (Cardiac, anti-coagulation, PPIs)
- Imaging assessment of **pericardial fluid** presence
- **AEs**
- **12- Lead -ECG**
- Additional Assessments for **NA subset** subjects (non-SOC): **Cerebral MRI, neurological exam and neurological evaluation using the NIH stroke scale** within 72-hours post procedure, preferable prior to discharge. A certified/qualified physician expert must perform neurologic exams at pre-and post-ablation and possibly at other follow-up visits, pending previous findings of micro-emboli/neurologic deficits. For procedures on Friday a window of a maximum of 96 hours is justified. Cerebral MRI images will be transmitted to an independent

core laboratory. NOTE: Patient questionnaires will only be used in countries with validated languages.

- Additional Assessments for **EE subset** subjects (non-SOC): **Endoscopy** to check for any esophageal lesions and/or damage will be performed preferable prior to discharge and no later than 72- hours after procedure (for procedures on Friday a window of a maximum of 96 hours is justified). Endoscopy images will be transmitted to an independent core laboratory.

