*\*Note: The upper bound of the 3-month visit will be considered as the start point of the evaluation period of AAD failure, which is Day 105. As it is a common practice for medications to be adjusted and/or stopped during an in-clinic visit (i.e., 3-month follow-up visit), subject may have his/her medication adjusted or stopped during the CIP-defined follow-up window, including the Class I/III AADs.*

- **Use of a non-study device** for the purpose of PVI (i.e., touch-up) and/or for the ablation of left atrial non-PV AF targets (i.e., posterior wall) during index ablation procedure or within-lanking repeat procedures.
- **Acute reconnection:** any reconnection in the PVs that are identified after adenosine/isoproterenol challenge among all targeted PVs.

- **Repeat ablation procedures** for left atrial arrhythmia (AF, AT or AFL of unknown origin\*) within the 12-month FU period. Procedures for CTI dependent flutter in the follow-up period are not considered repeat procedures per CIP.
- **Quality of Life (QoL):** defined as the change of QoL which is assessed by comparing the Atrial Fibrillation Effect on Quality-of-Life (AFEQT™) scores before and at 3, 6 and 12- months after the ablation procedure.
- **Hospitalization for cardiovascular events** through 12-month follow-up compared to 12 months prior to baseline.

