## **7.11 Additional Endpoint Analyses**

No formal statistical hypothesis will be formulated and performed for the additional endpoints. Descriptive statistics will be provided on all additional endpoints in the analysis sets specified below.

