### **7.11.3 Additional Effectiveness Endpoints**

The additional effectiveness endpoints will be summarized descriptively in the PP and mITT analysis sets after all study subjects completed their 12-month follow up.

- **Single Procedural Success:** The number and percentage of subjects with single procedural success will be summarized. Kaplan-Meier estimates and plots will be used to characterize the time to first documented symptomatic atrial arrhythmia (AF, AT or AFL) recurrence following a single index ablation procedure.
- **Freedom from documented symptomatic atrial arrhythmia (AF, AT or AFL of unknown origin\*):** Kaplan-Meier estimates and plots will be used to characterize the time to first documented symptomatic atrial arrhythmia (AF, AT or AFL of unknown origin\*) recurrence based on electrocardiographic data ( $\geq 30$  seconds on arrhythmia monitoring device) during the effectiveness evaluation period (Day 91-Day 365).
- **Freedom from documented (symptomatic and asymptomatic) atrial arrhythmia (AF, AT or AFL of unknown origin\*) with additional failure modes:** Kaplan-Meier estimates and plots will be used to characterize the time to first documented (symptomatic and asymptomatic) atrial arrhythmia (AF, AT or AFL of unknown origin\*) based on electrocardiographic data ( $\geq 30$  seconds on arrhythmia monitoring device) during the effectiveness evaluation period (Day 91-Day 365).

The event-free rate will also be summarized descriptively as the number and percent of subjects free from documented (symptomatic and asymptomatic) atrial arrhythmia (AF, AT or AFL of unknown origin\*) during the evaluation period.

- **Use of a non-study device:**

- The number and percentage of subjects and number and percent of PVs ablated by a non-study catheter (NSC) for PVI will be summarized.

- Rate of ablation by NSC for PVI among all targeted pulmonary veins during index procedure:

$$= \frac{\text{Number of PVs ablated by NSC}}{\text{Number of ablated PVs}}$$

- Rate of ablation by NSC for PVI among subjects during index procedure:

$$= \frac{\text{Number of subjects with at least one PV ablated by NSC}}{\text{Total number of subjects ablated for PVI}}$$

- Ablation of left atrial non-PV AF targets (i.e., posterior wall) during index ablation procedure or for repeat procedures during the blanking period.

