Baseline AFEQT scores and changes from baseline at each timepoint the questionnaire is administered will be summarized descriptively for the following five scores. The overall AFEQT score and subscale scores across study visits will also be plotted.

- Overall AFEQT Score (18 questions)
  - Symptom Subscale Score (4 questions)
  - Daily Activities Subscale Score (8 questions)
  - Treatment Concern Subscale Score (6 questions)

- Treatment Satisfaction Score (2 questions)
- **Hospitalization for cardiovascular events:** The number and percentage of subjects and number and percent of hospitalization for cardiovascular event will be summarized.

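### The cardiovascular hospitalisation endpoint is a before/after comparison, but the SAP plans only crude counts that ignore follow-up time and leave stays arising from study procedures unaddressed

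*SAP*

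**What the plan says.** Protocol 7.3.3 defines the endpoint as "Hospitalization for cardiovascular events through 12 months follow-up compared to 12 months prior to baseline". SAP 7.4.4.3 keeps the comparison: "through 12-month follow-up compared to 12 months prior to baseline".

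The analysis is one sentence in SAP 7.11.3: "The number and percentage of subjects and number and percent of hospitalization for cardiovascular event will be summarized". The analysis sets are PP and mITT ("The additional effectiveness endpoints will be summarized descriptively in the PP and mITT analysis sets"), and the whole family of endpoints is descriptive ("Descriptive statistics will be provided on all additional endpoints in the analysis sets specified below").

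A note in Protocol 7.3.3 says what counts: "hospitalization is defined as prolonged stay > 2 nights post index ablation procedure or in-patient stay not concurrent with index ablation procedure", the latter lasting more than one calendar day. It leaves out emergency-room visits without admission and stays for social or administrative reasons. For the earlier period, Protocol 13.2.1 says that "information on hospitalization for cardiovascular reason (including arrhythmia, cardioversion, ...) from 12 months prior to enrollment will be collected from medical records". For follow-up, Protocol 13.5.2 collects cardiac-related hospitalisations and cardioversions at the 1-, 3-, 6- and 12-month visits.

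**The concern.** A before/after endpoint needs both periods described on a common footing, even when nothing is tested. The SAP sentence does not mention the earlier period and takes no account of how long each subject was observed. The omission is specific to this endpoint: the AFEQT bullet beside it asks for baseline and change from baseline, and the repeat-ablation bullets give explicit fractions.

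Two things could then distort the comparison, in opposite directions.

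- **Time at risk.** The earlier period is a full 12 months for everyone. The later one is cut short for dropouts and for subjects whom the plan follows for only 3 months. Raw counts after ablation come out too low, which flatters the device.
- **Stays arising from study procedures.** The same 30 subjects undergo the Day 75 re-map, cerebral MRI and endoscopy. If any of these leads to an in-patient stay or a longer index stay, the protocol note does not say to leave it out. That would add events after ablation.

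At stake is the reading of one supportive outcome in the final report. Study success and the hypothesised endpoints are not affected.

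**Working it through.** The plan gives no rate, effect size or sample size for this endpoint, so there is no figure of its own to reproduce. The check compares the provisions and then illustrates their size.

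**1. Who is under-observed after ablation**

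- Protocol 19.4.2: discontinued subjects (catheter inserted, no energy delivered) are followed for 3 months. Under SAP 5 they remain in mITT, one of the two sets used here. They are not in PP.
- Protocol 13.3.3: subjects needing commercial RF ablation outside the PV/CTI regions after catheter insertion are followed for 3 months.
- Dropouts may be in either set. SAP 7.8 gives missing-data rules for the primary and secondary endpoints only.
- SAP 7.1.2 and 7.1.3 remove non-system-related discontinuations and the commercial-RF cases from long-term effectiveness analyses, but do not say whether hospitalisation is one of these. Subjects discontinued for system-related reasons are not removed.

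Observed time relative to 365 days: 90/365 = 0.247 for a subject followed for 3 months. The 12-month visit window gives 335/365 = 0.918 to 379/365 = 1.038.

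**2. Size of the time-at-risk effect**

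Assumptions, not in the documents: a Poisson hospitalisation rate λ that is the same before and after; a share s of subjects followed for 90 days; everyone else followed for 365.

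- Ratio of post to pre events = (1 − s) + s × 90/365.
- s = 0.05: 0.95 + 0.012 = 0.962. s = 0.10: 0.925. s = 0.15: 0.85 + 0.037 = 0.887. So about 4% to 11% fewer events with no true change.
- Share with at least one event: before, 1 − exp(−λ); after, (1 − s)(1 − exp(−λ)) + s(1 − exp(−λ × 90/365)).

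| λ per year | Before | After, s = 0.05 | After, s = 0.15 |
|---|---|---|---|
| 0.2 | 18.1% | 17.5% | 16.1% |
| 0.4 | 33.0% | 31.8% | 29.4% |
| 0.8 | 55.1% | 53.2% | 49.5% |

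Using observed time removes the artefact. With 135 subjects, λ = 0.4 and s = 0.10, there are 135 × 0.4 = 54.0 events before and 54.0 × 0.925 = 49.9 after. Patient-years after ablation are 135 × 0.925 = 124.8, and 49.9/124.8 = 0.40 per patient-year, unchanged.

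**3. Stays arising from study procedures**

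- The same 30 subjects form all four subsets (Protocol 7.1), and 30/135 = 22.2%.
- The re-map is an invasive procedure at Day 75 ± 15 (Protocol 7.2.4), not concurrent with the index procedure.
- Endoscopy "will be performed preferable prior to discharge and no later than 72- hours after procedure", with 96 hours allowed after a Friday procedure. MRI has the same limits. A subject kept in for 72 or 96 hours stays about 3 or 4 nights, above the two-night threshold.
- The carve-out for planned admissions in Protocol 14.1.2 applies to serious adverse events only.

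If a fraction f of the 30 had a counted stay, independent of other events, the share with an event after ablation is p + (30f/135)(1 − p), where p = 1 − exp(−λ). At λ = 0.4, f = 0.25 gives 36.7% and f = 1 gives 47.9%, against 33.0% before.

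**4. Interval between the periods**

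The earlier period ends at enrolment, which is consent (Protocol 20.2.1). The procedure may follow up to 60 days later, so up to 60 days belong to neither period. Adverse-event records need not fill this gap, because Protocol 14.1.1 does not count AF recurrence, or cardioversion for recurrence, as adverse events.

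**The case against.** The strongest reply is that this is missing wording on one descriptive bullet. SAP 7.4.4.3 states the comparison and SAP 7.4.4 sends the reader to 7.11, so an analyst would probably tabulate both periods. Protocol 19.4.6 plans no inferential statistics for additional endpoints. That sets the severity and rules out any need for a model. It does not supply the missing denominator or the follow-up time.

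Several stronger readings are tempting, and the documents do not support them.

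- **That the periods have different stated lengths.** Both are 12 months. Only observed time and anchor dates differ.
- **That the periods use different definitions.** The note in Protocol 7.3.3 sits under an endpoint naming both periods and is not restricted to follow-up, although its two-night limb can apply only after the index procedure. Protocol 13.2.1 is a collection instruction, and collecting broadly before applying the endpoint rule is ordinary practice. Cardioversions are also collected after ablation. What stands is that nothing says the rule applies to the earlier period.
- **That the study requires hospital stays.** No passage requires admission for MRI, endoscopy or re-map. Such a stay might also be judged not to be for a cardiovascular event, or to be administrative. What stands is that the note leaves the choice open.
- **That the comparison is uninterpretable.** A shortfall of 4% to 11% does not show that.

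The SAP may also drop some subjects with short follow-up. That narrows the time-at-risk problem but does not remove it for dropouts or for system-related discontinuations in mITT.

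**Conclusion.** The point holds as a cheap improvement of low severity. The endpoint is a before/after comparison, and the planned summary neither makes that comparison nor allows for shorter observation after ablation. As written, it understates post-ablation events in the device's favour. The size depends on attrition: about 4% to 11% fewer events if 5% to 15% of subjects are seen for 90 days only, with a constant rate. Those shares and rates are illustrative; the documents give none for this endpoint.

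Stays arising only from study procedures could push the other way. The figure of 30/135 (22%) is an upper bound that needs every subset subject to have a counted stay and none to have another event. With all 30 counted at a rate of 0.4 per year, the rise is about 15 points (33.0% to 47.9%). How many would be admitted is unknown.

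**What to change.** Replace the hospitalisation bullet in SAP 7.11.3 with text to this effect:

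- For each period (12 months before enrolment; index procedure to last follow-up, at most 365 days), report the number of subjects with an event, the number of events, and events per patient-year using the time actually observed. State the denominator of every percentage.
- Apply the in-patient rule of Protocol 7.3.3 to both periods. Show index stays beyond two nights on their own line, since they have no counterpart before ablation.
- List separately, outside the comparison, any stay or extra nights due only to study-required MRI, endoscopy or re-mapping.
- State that the interval from consent to procedure (up to 60 days) is in neither period, or report it separately.
- Say whether the exclusions in SAP 7.1.2 and 7.1.3 apply to this endpoint.

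Keep the analysis descriptive; no regression model or test is needed. The cost is SAP wording, minor extra programming and possibly one eCRF field for the reason for stay, if it is not already captured.

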## 7.12 Subset Analyses

The same subjects are selected for all four (4) subsets, which include a PVI Durability subset, a Neurological Assessment (NA) subset, a Cardiac Computed Tomography (CT) or Magnetic Resonance Angiogram (MRA) image subset and an Esophageal Endoscopy (EE) subset.

The subset endpoint analysis will be summarized in corresponding subset after all study subjects have completed their 3-month follow up. The analysis results will be presented in the 3-Month CSR. If there are any status change of the endpoint outcome after 3-Month CSR, descriptive summaries will be updated using the 12-month follow-up data and reported in the final CSR.

### 7.12.1 Analysis of PVI Durability Endpoint

Percentage of targeted PVs in the index ablation procedure being durably isolated as confirmed by the electroanatomical mapping 75 days (+/- 15 days) post index ablation procedure.

Percentage of subjects with durably isolated targeted PVs, as confirmed by the electroanatomical mapping at 75 days (+/- 15 days) post index ablation procedure.

These analyses will be performed in the PVI Durability Analysis Set.

### 7.12.2 Analysis of NA Endpoint

The following analyses of neurological evaluations will be conducted and summarized descriptively. The analysis will be performed in the Neurological Analysis Set.

In addition to the criteria stated below, subjects will undergo full neurological follow-up only if neurologic symptoms and/or cerebral ischemic lesions are identified in a prior evaluation; results for these additional neurological evaluations will be summarized descriptively.

- **Neurological Exam:** The incidence of new or worsening neurological deficits post-ablation compared to pre-ablation will be summarized descriptively by timepoint.
- **Cerebral Emboli:** The frequency, anatomical location (side and area), and size (diameter and volume) of asymptomatic and symptomatic cerebral emboli observed pre-ablation and new emboli observed post-ablation as determined by MRI evaluations by the core lab will be summarized descriptively by timepoint.
- **Mini Mental State Examination (MMSE):** MMSE scores pre-ablation and change from pre-ablation at the 1-month follow-up will be summarized descriptively and plotted by timepoint.
- **National Institute of Health Stroke Scale (NIHSS):** NIHSS scores pre-ablation and post-ablation prior to discharge will be summarized descriptively and plotted by timepoint.
- **Modified Rankin Scale (mRS):** mRS scores pre-ablation and change from pre-ablation at the 1-month follow-up will be summarized descriptively and plotted by timepoint.

